7. TRIAL DESIGN

The study consists of 2 parts. The first consists of collecting data about the use of an app for phone-based 6MWT, the “Timed Walk” app, during the outpatient consultations (via phone or in clinic). These data will be used to understand if patients are using the app and if the measurements produced by the app are being used for clinical decisions. The data will be collected on an electronic spreadsheet, using a coding schema, which will be analysed every 3 months for quality assurance and at the end of the study for the final statistics.

The second part of the study will involve a sample of 15 patients who will be sent a trundle wheel and will be invited to perform 10 6MWT using the app and the trundle wheel simultaneously. The data collected in this way will be used to A) assess the accuracy of the app measurement and B) create a public anonymised dataset for the development of future algorithms for the 6MWT. The same group of patients will also be invited to answer a questionnaire about the usability and acceptance of the app and will be interviewed about the same topics.

This study is a collaboration between the Oxford University Hospital (OUH) Trust and Malmo University, Sweden. Malmo University is the main developer and maintainer of the Timed Walk app, and their interest focuses on the accuracy and usability of the app. The OUH Trust is, on the other hand, interested in using the app to remotely monitor their cardiac patients and assessing its impact on the management of those patients. Malmo University will therefore offer engineering work both in terms of the app and data analysis and OUH will recruit patients and collect data.

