8.2. Inclusion Criteria

- Participant is willing and able to give informed consent for participation in the study.
- Male or Female, aged 18 years or above.
- Under the care of the cardiovascular clinic at OUH Owning or having access to a smartphone with either Android or iOS
- Being able to use a smartphone app
- Being able to walk

A subgroup of 15 patients will be identified among those who are more willing to use the app to perform the additional measurements with the trundle wheel and to answer the questionnaire. This group should include a balanced representation of age groups and sexes.

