9.2. Screening and Eligibility Assessment

Patients will be screened every week according to the scheduled clinic phone calls or visits. A list of candidates who match inclusion and exclusion criteria (except use of smartphone) will be prepared before consultation.

During the consultation, patients will be asked about their access and fluency with smartphones to further verify compliance with the criteria.

The subgroup of 15 patients will be chosen among those using the app depending on the frequency of their use of the app and general willingness to participate in the study.

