Fifteen patients will be selected based on their ability and engagement and invited to perform 10 additional 6MWT using the app and a trundle wheel simultaneously. An additional informed consent form will be sent to these patients. To those who accept, the research team will send a pre-packaged trundle wheel.

At the end of each of these tests, patients will need to share the raw data collected by the phone during the test through the app's "share" button. When prompted, users will choose to share the data through email and send them to a special address that will be set up for the purpose in Malmö. The app will automatically attach to these emails the data it used to compute the distance including the patient's geographical position (longitude, latitude, altitude, speed) and inertial sensors data (acceleration, inclination, detected steps). Patients will be instructed to also add the distance measured by the trundle wheel to the message for reference.

In order to study the accuracy under different conditions, patients will be instructed to perform 5 tests walking along paths the shape of which is known to obtain the best distance estimation (straight or gently curved paths). Patients will also perform 5 more tests walking over paths that may be more "challenging" for the app, for example those including narrow curves, U-turns or in confined spaces.

If less than 15 trundle wheels are purchased for the study, patients will be asked to send the meters back to the clinical centre once the 10 tests are completed. Trundle wheels will be then cleaned and disinfected and sent to another batch of patients until covering 15 subjects.

Towards the end of the study, patients of the subgroup will be sent an online questionnaire related to usability and acceptance to be filled in electronically. The questionnaire will be based on the validated and widely used uMARS questionnaire¹² and the Mobile Health Technology Acceptance Model (MoHTAM) questionnaire¹³.

Five to ten patients will be selected for an additional phone-based short interview. Notes from the interview will be taken and voice will be recorded if technically possible. The interview will aim at

¹² <https://mhealth.jmir.org/2016/2/e72/>

¹³ <https://ieeexplore.ieee.org/abstract/document/6149947>

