13. DATA MANAGEMENT

13.1. Data Recording and Record Keeping

Part1

The data will be collected using an electronic spreadsheet shared by the team at OUH. Patients will be asked about their recent app-based 6MWTs during visits or phone calls and will be invited to share the log of their app-based 6MWTs by email or telephone with the clinician. If patients have technical problems and need assistance, they can contact the team in Sweden, who are responsible for the development of the Timed Walk app. In this case, the patient can disclose their identity to the team in Sweden if they wish.

Every 3 months, the spreadsheet will be anonymised by substituting the patient hospital number with an internal ID and sent to Malmo University for analysis in an encrypted email.

Part 2

Results of the additional 6MWTs performed by the subgroup of 15 patients will be shared by email with the team in Malmo. We will seek explicit consent to share these data, both as identifiable information for the researchers in Sweden and in an anonymous format publicly.

In order to anonymise the data before publication, the following strategy will be used:

- Email addresses will be removed and an internal patient ID will be used to group tests belonging to the same user.
- Timestamps will be formatted only in relation to the start of the test.
- Location data will be anonymised using a random offset on both longitude and latitude (resulting in the trace to keep its original shape, but the position to be placed in a random place).
- Any unique identifier of the phone will be removed, but the make and model may be kept in order to compare different phones characteristics.

Electronic questionnaires for usability and acceptance will be set up using Microsoft Forms. Malmo University has an agreement with Microsoft to use the product for research purposes and guarantees

that data is protected according to the GDPR. The questionnaire will not require personal information to be collected and will be deleted after analysis.

Audio recording of the interviews will be collected by OUH and sent electronically to Malmo University for analysis. These files will not be linked to the identity of the patient, they will be transcribed and deleted immediately after. All files containing patients' anonymised data exchanged between Malmo and OUH will be encrypted using a password which will be communicated verbally during a phone call.

Paper forms will be kept by the Principal Investigator at OUH.

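### Usability and acceptance are scored only by 15 app users chosen for willingness and engagement, and the interviews on non-use come from the same group

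*Combined protocol and SAP*

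**What the plan says.** The rule for choosing the Part 2 patients appears in three places:

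- Section 8.2: "A subgroup of 15 patients will be identified among those who are more willing to use the app".
- Section 9.2 (Screening and Eligibility Assessment): "The subgroup of 15 patients will be chosen among those using the app depending on the frequency of their use of the app", together with general readiness to take part.
- Section 9.3 (Subsequent Visits): "Fifteen patients will be selected based on their ability and engagement and invited to perform 10 additional 6MWT".

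The one counterweight is in section 8.2: "This group should include a balanced representation of age groups and sexes".

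The questionnaire is confined to this group. Section 7 says "The same group of patients will also be invited to answer a questionnaire about the usability and acceptance of the app", and section 9.3 says "patients of the subgroup will be sent an online questionnaire related to usability and acceptance". Section 7 also has the same group interviewed. Section 9.3 sets the number of interviews at 5 to 10 and gives their aim as finding out why people do or do not use the app.

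The objective in section 6 carries no restriction to engaged users. Section 12.1 plans descriptive statistics of the questionnaires and a thematic analysis of the interviews. Section 12.2 defends the number 15 as usual for usability studies, and does not discuss how the 15 are picked.

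**The concern.** A questionnaire on whether people accept the app is given to people chosen partly because they have already accepted it. A favourable score could then reflect the selection rule as much as the app, and a reader could not separate the two. Infrequent users, people who installed the app and stopped, and people with technical trouble have the most to say about what needs improving, and the rule makes them unlikely to be asked.

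The interviews have a sharper form of the same problem. Reasons for non-use are part of their aim, yet section 9.2 limits the subgroup to people using the app.

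What is at stake is one secondary objective, usability and acceptance. The primary uptake percentage is counted in all Part 1 participants and is not affected.

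**Working it through.** The plan gives no formula, SD or precision target for the 15, so there is no figure of its own to reproduce. The check sets the text side by side and then illustrates the size.

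**Selection against outcome.** The grounds for selection are willingness (8.2), frequency of use and willingness (9.2), and ability and engagement (9.3). The outcome is usability and acceptance scored by the same people (7, 9.3). All three rules favour engaged users, and no other usability or acceptance questionnaire is planned.

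**Fraction selected.** The synopsis gives 250 to 500 participants: 15/500 = 3% and 15/250 = 6%. The proper reference group is app users, which may be smaller. If half use the app (an assumption), the pool is 125 to 250, and the fraction is 15/250 = 6% to 15/125 = 12%.

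**Possible shift.** Let m be the mean engagement of those selected, in SD above the mean of the pool, and r the correlation of engagement with the questionnaire score. Then

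shift in SD of the score = r × m.

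If the 15 were literally the most engaged of N people with normally distributed engagement, simulation gives m = 1.97 for N = 250 and 2.25 for N = 500. For a milder rule, with selection anywhere in the top 20%, m = 0.2800/0.20 = 1.40 (normal density at the 80th percentile divided by the tail area). The values of r are assumptions; the documents give none.

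| Selection | m | r = 0.1 | r = 0.3 | r = 0.5 |
|---|---|---|---|---|
| Top 15 of 250 | 1.97 | 0.20 | 0.59 | 0.98 |
| Top 15 of 500 | 2.25 | 0.23 | 0.68 | 1.13 |
| Within top 20% | 1.40 | 0.14 | 0.42 | 0.70 |

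(Products use m before rounding.)

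**Against sampling error.** The 95% half-width for a mean of 15 is t(0.975, 14)/√15 = 2.145/3.873 = 0.55 SD. The shift reaches that size at r = 0.554/2.25 = 0.25 or r = 0.554/1.97 = 0.28 under strict top-15 selection, and at r = 0.554/1.40 = 0.40 under the milder rule. More patients chosen the same way would narrow the interval without removing the shift.

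**Interviews.** The aim covers use and non-use (9.3). The source is the Part 2 group (7), taken from people using the app (9.2). As written, the group holds no non-users to explain non-use.

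**The case against.** Several points on the other side stand.

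- No section says that the most frequent users are taken. The wording in 9.2 is "chosen among those using the app depending on the frequency of their use of the app", and the age and sex balance works against a strict ranking. The top-15 rows of the table are therefore an extreme case.
- The direction is likely but not certain. Patients answer after being asked for ten extra tests, five of them on routes that are hard for the app, which could lower scores. A bounded scale would also limit large upward shifts.
- Part 1 covers some of the ground. Uptake is counted in everyone, and APP-ISSUE entries and reasons for refusal or withdrawal are logged. These do not replace questionnaire scores from ordinary users.
- The Part 2 analyses are descriptive, and nothing says that they will be extrapolated to all participants. A stated limit on scope would be a minimum answer, but the objective would still be wider than the data.
- Handling a wheel, completing ten tests and sharing raw data are practical reasons to choose engaged patients. That supports the wheel subgroup. It does not explain why an online form goes to no one else.

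Two stronger readings are tempting. A reader might infer that error against the wheel is understated because patients with poor readings drop out of use. The documents do not show this. No rule excludes patients with an APP-ISSUE entry, and Part 1 patients walk without a reference distance, so they would often not know that a reading was wrong. The example given for that code is a crash, which yields no distance rather than a wrong one. Half of the wheel tests are on difficult routes.

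A reader might also infer that a planned comparison of phones is compromised. Section 13.1 says only that "make and model may be kept in order to compare different phones characteristics", within the anonymisation steps for the public dataset. Section 12.1 specifies no phone comparison.

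**Conclusion.** The point holds for the questionnaire and the interviews. Usability and acceptance will be measured only in 15 users chosen on traits close to the outcome, so the scores are likely to be more favourable than among app users in general. The size cannot be determined from the documents. It is about 0.2 to 1.1 SD if selection is near the top and r lies between 0.1 and 0.5, and about 0.1 to 0.7 SD under the milder rule. The mismatch between the aim of the interviews and their source rests on the text alone and needs no assumption.

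For accuracy, the supportable statement concerns scope: the results will describe engaged users, with age and sex the only stated balance.

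**What to change.** In section 9.3, with matching changes in section 7 and Appendix B:

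1. Have the hospital team send the existing online questionnaire to all Part 1 participants with an APP-OK or APP-ISSUE code. The hospital team should send it because the Swedish team receives Part 1 data only without identities.
2. Add one self-reported item on the number of app tests done, so that the form stays anonymous. Give the 15 a separate copy of the form so that their answers can be told apart.
3. In section 12.1, report scores by level of use and separately for the 15, with the response rate.
4. Keep 5 to 10 interviews, but draw some from participants with few or no app tests or an APP-ISSUE entry.

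As a lesser change, keep the wheel subgroup at 15, add phone platform (Android or iOS) to the age and sex balance where feasible, and state that the accuracy results apply to engaged users.

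The cost is a change to the information sheet and consent form and one more mailing of a form that is already planned. Low users will probably respond less often, so non-response should be reported and considered when the scores are read.

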6. OBJECTIVES AND OUTCOME MEASURES

The population to be studied is composed of hospital outpatients who have conditions where the 6MWT is routinely used in clinical care, and/or are using the 6APP as an alternative.

The objective is: To evaluate the usefulness of adopting remote, mobile-based 6MWT among hospital outpatients, within the constraints imposed by the SARS-COV2 pandemic.

Objectives	Outcome Measures	Timepoint(s) of evaluation of this outcome measure (if applicable)
Primary Objective To assess whether patients are able and willing to use a smartphone app for the 6MWT	Percentage of participants who perform at least one app-based 6MWT before patient consultation.	At 3, 6, 9 and 12 months after the start of the study.
Secondary Objectives To assess the accuracy of the app-based measurement. To assess whether differences in distance walked according to the app altered management of patients.	Comparison of walked distance (6MWD) measured by the app versus a trundle wheel reference. Number of clinical investigations and multidisciplinary team discussion triggered by variations in app-based 6MWD.	12 months. At 3, 6, 9 and 12 months after the start of the study.

To assess the usability and acceptance of the app.	Standard usability and acceptance questionnaires, semi-structured interviews.	12 months.
To collect raw data from phones' sensors to allow the development of future algorithms for app-guided 6MWT.	Localisation position (GPS), speed, acceleration, step count, gyroscope samples collected during 6MWT.	12 months.
To determine whether the use of the 6MWT reduces time spent and number in hospital visits.	Time spent in hospital attendances and number of hospital visits made during use of the 6MWT compared with previous periods.	12 months.
To compare the use of 6MWT during pandemic with pre-pandemic use.	Total number of 6MWTS performed during 2020 pandemic period compared with pre-pandemic period.	12 months.

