12. STATISTICS

12.1. Description of Statistical Methods

The analysis of the data involves reviewing the spreadsheet. The use of the labels will simplify analysis and will avoid manual coding. The R programming environment will be used to compute statistics.

To assess whether patients are able and willing to use a smartphone app for the 6MWT.

For each recruited patient, we will compute the number of app-based 6MWT results available since they confirmed that they have downloaded the app. From this number, we will compute a histogram of the number of available app-based 6MWT per patient and the percentage of participants who perform at least one app-based 6MWT prior to every consultation.

To assess the accuracy of the app-based measurement.

We will compare the walked distance measured by the app with the distance measured by the trundle wheel for those tests that provide both information. We will compute descriptive statistics (mean, standard deviation, percentiles) of the difference and BlandAltman plots.

To assess whether differences in distance walked according to the app altered management of patients.

We will use the codes related to clinical evaluations to compute descriptive statistics about the frequency of those evaluations and about how many of them were triggered by observed changes of the 6MWD.

To assess the usability and acceptance of the app.

We will compute descriptive statistics of the results of the usability and acceptance questionnaires. We will use thematic content analysis to analyse the interview transcripts.

To collect raw data from phones' sensors to allow the development of future algorithms for app-guided 6MWT.

We will also use the sensors data sent from patients involved in part 2 of the study to identify strategies to improve the algorithm that computes the distance. The availability of this type of data would be unique and would open interesting research in computer science and biomedical engineering. The University of Malmo is planning to experiment signal processing (Kalman filters, FIR filters) and machine learning (LSTM RNN) techniques to improve the accuracy of the current GPS-based algorithm and to explore the possibility to develop an indoor version of the algorithm based purely on the inertial sensors (acceleration).

To determine whether the use of the 6MWT reduces time spent and number in hospital visits.

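### The trundle wheel is the sole reference for app accuracy, yet the protocol describes no check of a wheel against a known length and no record of which wheel was used

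*Combined protocol and SAP*

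**What the plan says.** Section 6 lists app accuracy as a secondary objective, with this outcome: "Comparison of walked distance (6MWD) measured by the app versus a trundle wheel reference". No second measure of distance is named anywhere.

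The procedure is in section 9.3 (Subsequent Visits), Part 2: "Fifteen patients will be selected based on their ability and engagement and invited to perform 10 additional 6MWT using the app and a trundle wheel" at the same time. To those who agree, "the research team will send a pre-packaged trundle wheel". Return and reuse are conditional: "If less than 15 trundle wheels are purchased for the study, patients will be asked to send the meters back to the clinical centre" after their tests. Then: "Trundle wheels will be then cleaned and disinfected and sent to another batch of patients until covering 15 subjects". The number of wheels is not fixed.

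The reference value is reported by the patient: "Patients will be instructed to also add the distance measured by the trundle wheel to the message for reference". No wheel number is requested.

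For the analysis, section 12.1 says: "We will compare the walked distance measured by the app with the distance measured by the trundle wheel for those tests that provide both information". It continues: "We will compute descriptive statistics (mean, standard deviation, percentiles) of the difference", together with Bland-Altman plots. There is no term for the wheel.

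The quality checks in section 14 cover the spreadsheet codes and suspected inaccuracy or misuse of the app. They do not mention the wheel.

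**The concern.** In an agreement study, the error of the reference becomes part of the reported error of the method under test. That is acceptable when the reference error is known to be small or has been measured. Here it is neither stated nor measured. The typical fault of a measuring wheel is a scale error, such as a slightly wrong circumference, which repeats in the same direction and proportion on every walk. Repeating the walk 10 times with the same wheel does nothing to reduce it.

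Two results are exposed. The mean difference could carry a bias that belongs to the wheels. The limits of agreement could be widened by differences between wheels and then be read as the app performing differently from patient to patient.

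The problem also outlasts the study. Sections 7 and 13.2 plan a public dataset for algorithm development. Under the anonymisation rules in section 13.1, tests are grouped by an internal patient ID and times are kept only relative to the start of each test. Unless a wheel number is stored, later users could not tell which patients shared a wheel, and an algorithm tuned to these distances could absorb a wheel's error.

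**Working it through.** The plan states no wheel tolerance, accuracy margin or precision target for Part 2, so there is no figure to reproduce. The check is error propagation.

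**Inputs from the documents**
- 15 patients with 10 walks each (section 9.3, Part 2): 15 × 10 = 150 paired walks.
- A 420 m walk, taken from a sample log entry in the event-code table of section 9.3. It is an illustration and not a planning value.

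**Assumed inputs**
- Wheel scale error e of 1%, 2% or 3%.
- Between-wheel SD s of 2%.
- Number of wheels k of 1, 3, 5 or 15, used equally.

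**Model**
Let D be the true distance, a the app error and e the wheel's scale error. The app reads D + a and the wheel reads D(1 + e). Then

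app − wheel = a − D·e.

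The data contain only this combination, so a and D·e cannot be separated without outside information on e. The phone's GPS trace does not supply that information, because it is the app's own input.

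**Step 1: shift from one wheel (D·e at 420 m)**
- 1%: 420 × 0.01 = 4.2 m
- 2%: 420 × 0.02 = 8.4 m
- 3%: 420 × 0.03 = 12.6 m

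A wheel that reads high makes the app look as if it under-reads, and the reverse. The shift applies to every walk made with that wheel: 150/15 = 10 walks with 15 wheels, 150/5 = 30 with 5, 150/3 = 50 with 3, and all 150 with one.

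**Step 2: effect on the overall mean difference**
If wheel errors are independent with SD s, the SD of the mean difference due to wheels alone is D·s/√k. At s = 2%:
- k = 1: 8.4/√1 = 8.4 m
- k = 3: 8.4/√3 = 4.85 m
- k = 5: 8.4/√5 = 3.76 m
- k = 15: 8.4/√15 = 2.17 m

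The number of walks per wheel does not enter the formula. Only more wheels, or knowledge of e, reduces this term. If all wheels share the same error, for example as one faulty batch, √k gives no protection and the full D·e remains as bias.

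**Step 3: effect on the limits of agreement**
A perfectly accurate app was simulated (a = 0, D = 420 m, s = 2%, 150 walks, 4,000 runs). The average half-width of the apparent limits of agreement, 1.96 × SD of the differences, was:
- k = 1: 0 m (all of the wheel error appears as bias)
- k = 3: 11.78 m
- k = 5: 13.88 m
- k = 15: 15.67 m

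More wheels therefore move the error from the mean into the spread. Neither summary is free of it.

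**The case against.** Much can be said against making more of this, and most of it stands.

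- **Reuse is not certain.** A reader might infer from the sentence on cleaning that wheels will circulate. Section 9.3 makes this conditional on fewer than 15 being bought. With 15 wheels no return is planned, although each wheel's error still runs through its own patient's 10 walks.
- **Silence is not refusal.** A reader might infer that no check will be made. The documents only fail to describe one. Section 14 refers to standard operating procedures that are not part of the documents, and a wheel check could sit there.
- **The size is unknown.** Nothing suggests that any wheel is wrong by 1%, 2% or 3%.
- **The 42 m figure is not a fair yardstick.** It is tempting to set 12.6 m against the 42 m in section 5.2. But 42 m is a threshold for change over time, and section 5.4 says that the app is used to follow trends. Even if a 3% wheel error were mistaken for a 3% app error, its effect on a 42 m change would be 42 × 0.03 = 1.26 m. The wheel readings are also collected only in Part 2.
- **Errors average across wheels.** With 15 independent wheels and s = 2%, the SD on the mean is only 2.17 m. This holds for independent errors only, and it does not help the limits of agreement.
- **Some comparisons are protected.** For one patient with one wheel, favourable minus challenging paths leaves only e times the difference in distance, so the error largely cancels.
- **No decision turns on it.** Accuracy is a descriptive secondary outcome with no margin or pass/fail rule.

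What remains is that the reported app error contains an unmeasured wheel component, and nothing described in the plan would allow it to be removed later.

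**Conclusion.** The point holds as a modest design weakness. The wheel is the only reference, no length check or wheel identifier is described, and the analysis attributes the whole app-minus-wheel difference to the app. The possible shift is proportional to a wheel error that the documents do not give, so the metre values above illustrate a range and do not estimate an actual bias. How the error shows itself depends on the number of wheels: entirely as bias with a single wheel or a fault common to all, and partly as wider limits of agreement with several independent wheels.

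The documents do not support the conclusion that the accuracy result will be wrong, that unchecked wheels will certainly be shared, or that patient management is at risk. The case for acting is that the correction is cheap and that wheel identity may not be recoverable if it is not recorded at the time.

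**What to change.** In section 9.3 (Subsequent Visits), Part 2, add the following:

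1. Number each wheel. Before posting, and again on return where wheels are returned, roll it along one measured length L at the hospital and log the reading R. L should be long enough for the wheel's reading resolution to be small relative to the tolerance.
2. Record at dispatch which wheel each patient receives. Keep that number with each test in the study data and in the public dataset.
3. Fix a tolerance in advance. For a wheel outside it, either rescale its readings by L/R or exclude them, with the choice stated beforehand. Under the model above R = L(1 + e), so D(1 + e) × L/R = D and the scale error is removed.

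In section 12.1, state that the app-minus-wheel differences use the checked or rescaled wheel distances, and report the check readings beside the Bland-Altman results.

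The cost is a few minutes per wheel, possible unpacking and repacking if wheels arrive already packaged, and one data column. Patients do nothing extra. If wheels are not returned, only the check before posting is possible. The check does not deal with how patients handle the wheel, with turns on the challenging paths, or with errors in self-reported readings; those remain limitations to report.
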